### 3 Study Design, Efficacy Endpoints, and Sample Size Determination

#### 3.1 Study Design

For the purpose of exploring the above objectives, the study will be conducted as a randomized, double-blind, sham-controlled dose finding study in SARS-CoV-2 infected outpatients with mild-to-moderate COVID-19.

This dose ranging portion of the study plans to enroll a minimum of 60 volunteers who are seronegative for SARS-CoV-2 Spike IgG antibody at baseline with 30 in each of at least two dosing cohorts (20 assigned to RD-X19 and 10 assigned to sham per cohort, 2:1 randomization).

Cohort A will begin with 24 J/cm^2 per treatment, administered 2X/Day for duration of 7 days. Once 80% of subjects (n=24) in Cohort A complete the Day 8 visit and no predefined safety signals as outlined in the study pausing/stopping criteria have been observed, Cohort B, 32 J/cm^2 per treatment will start enrollment. In the event device-related serious adverse events or patterns of device-related adverse events, including application site reactions, are observed in Cohort A, and based on the review and recommendation of the external safety monitoring committee (SMC) of unblinded data, the study may proceed with enrollment and dosing in Cohort C, 16 J/cm^2 per treatment in keeping with SMC recommendations. An illustration of the ascending (or descending) dose finding design is provided below.

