#### **Cohort C: RD-X19 16 J/cm^2 vs. Sham**

(5 minute treatment, 2X/Day for a duration of 7 days)

During the investigation of Cohort B, once 80% of the subjects complete the Day 8 visit without observation of safety signals meeting the definition of predefined pausing/stopping criteria, a blinded review of available safety data for Cohort A and Cohort B was conducted along with a blinded assessment of the proportion of 'success' events on the first primary endpoint of sustained symptom resolution for the subjects within each Cohort. At the sponsors option, the final cohort enrollment was increased in sample size, targeting up to an additional 150 subjects (2:1 randomization). This option to increase overall enrollment is intended to provide better resolution of the point estimate between a safe, well tolerated dose and sham treatment in a broader population, including subjects who are SARS-CoV-2 Anti-Spike IgG antibody positive at baseline, either through natural infection or immunization, in preparation for future trials.

**Note:** The Cohort which has the optional additional enrollment will be considered the 'Final Cohort'. In the event that the sponsor elects to not proceed with the optional additional enrollment then the last Cohort investigated will be defined to be the 'Final Cohort'. As such, the Final Cohort is defined as the cohort including the final randomized subject.

Subjects meeting all inclusion criteria and none of the exclusion criteria will be randomized in a 2:1 ratio within each dosing cohort.

The clinic visits will occur at:

- Visit 1 / Screening, Enrollment & Randomization
- Visit 2 / Day 3
- Visit 3 / Day 5 ( $\pm 1$  day)
- Visit 4 / Day 8 ( $\pm 1$  day)
- Visit 5 / Day 14 ( $\pm 2$  day) / Early Termination (ET)

Assessments of study subjects will occur on study days 1, 3, 5, 8, with the final assessment visit on Day 14. Telephonic outreach by study personnel will occur on days 2 and 4 for additional safety monitoring and to enhance compliance with at-home study procedures. Study subjects

requiring hospitalization will be tracked until discharge or death and the date and time of these events will be captured in the study data.

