### 3.3 Sample Size Determination

The target number of subjects to be randomized per cohort is 30 individuals seronegative for SARS-CoV-2 Spike IgG antibodies (20 subjects to the RD-X19 treatment arm and 10 subjects for Sham control), for a minimum total of 60 subjects. At the sponsors option, the total number of subjects can be increased by an additional 150 total subjects to include all serostatuses after a dose has been selected based on adequate safety/tolerability observed for the final dose cohort.

Based on findings in the EB-P12-01, the hazard ratio observed for the time to sustained symptom resolution in that early feasibility trial was HR=0.4 between active RD-X19 and Sham.

The increased sample size in the Final Cohort (up to 180 total), with an anticipated roughly equal number of antibody positive to negative individuals enrolled during the option, will lead to approximately 90 seropositive and 90 seronegative subjects. The modified Full Analysis Set (mFAS) population containing only antibody negative subjects (as defined in Section 4, 60 RD-X19: 30 Sham) has at least 90% power to detect meaningful changes in SARS-CoV-2 symptom resolution from baseline (Hazard ratio of 0.4) for the first primary endpoint. These power calculations assume that testing will be carried out using  $\alpha = 0.025$  one-sided, up to a 20% dropout rate due to discontinuations or hospitalizations, as well as an assumption that the proportions of subjects having the event (for the first primary endpoint) by Day 14 is 85% for the RD-X19 arm and 75% for the Sham arm.

In the Full Analysis Set (FAS) for the Final Cohort, the primary analysis population including all randomized subjects receiving at least one treatment, the increased sample size (increase by a minimum of 100 RD-X19: 50 Sham) has at least 90% power to detect a Hazard ratio of 0.5 between RD-X19 and Sham for the first primary endpoint. These power calculations assume that testing will be carried out using  $\alpha = 0.025$  one-sided, as well as an assumption that the proportions of subjects having the event (for the first primary endpoint) by Day 14 is 90% for the RD-X19 arm and 85% for the Sham arm, with adjustment for multiple endpoints as described in Section 5.1.1.

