## 5 Planned Analyses

All study data will be presented in by-subject data listings. Tabulations will be displayed separately for RD-X19 and Sham from the Final cohort for the primary analysis, and, RD-X19

from each cohort individually, Pooled RD-X19 from both Cohorts and Pooled Sham from both Cohorts for supportive/secondary analyses.

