## 5.1 Methodological Considerations

### General Conventions

SAS software (version 9.4 or higher) will be used for all data analyses and tabulations.

Data for all investigational centers will be pooled for analysis. The sham groups from different cohorts will not be combined for the analyses unless otherwise specified. For all analyses, subjects will be analyzed based on actual treatment received.

Unless specified elsewhere, baseline is defined as the last available measurement prior to administration of study treatment. Change from baseline will be calculated as the post-baseline value minus the baseline value.

Summary tables will include the data based upon the protocol scheduled time points. For subjects who are early discontinued from the study or have visits outside of the allowed window, all efficacy assessments captured at the visit will be assigned to the protocol scheduled time point as follows:

Visit of Treatment Period	Range for ET / Visit Re-allocation*
Visit 2 / Day 3	Study Day 1 to 3
Visit 3 / Day 5 ( $\pm$ 1 day)	Study Day 4 to 6
Visit 4 / Day 8 ( $\pm$ 1 day)	Study Day 7 to 9
Visit 5 / Day 14 ( $\pm$ 2 day)	Study Day $\geq$ 10

\*Study day = date of visit - date of first treatment + 1

Descriptive statistics of continuous variables will include n, mean, standard deviation (SD), median, and range. Generally, the minimum and maximum values will be presented to the same decimal precision as the raw values, the mean and median values to one additional decimal, and the SD, to two more decimal places than the raw values. Summaries for categorical data will include frequencies and percentages. Percentages will be presented to one decimal place.

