  - Who have RR  $\geq 20$  at Baseline
  - Who report Shortness of Breath at Baseline, or
  - Who have clinical signs suggestive of lower airway involvement.
- 3) gender
- 4) age (grouping of <50,  $\geq 50$ )
- 5) baseline antibody status (positive, negative)

Note: For the second primary efficacy endpoint the term for baseline disease status of mild vs. moderate will not be included.

Two-sided 95% confidence intervals and two-sided 90% confidence intervals will also be derived for the hazard ratios from the above models.

Supportive analyses in each case for the two primary efficacy endpoints will be produced for the mFAS and the Per Protocol population. For the mFAS population the Cox proportional hazards regression model will not include the covariate related to baseline antibody status.

All of the above analyses of the primary endpoints will also be produced for pooled RD-X19 doses vs. pooled Sham, and for RD-X19 low dose (i.e., the dose not expanded to produce the Final Cohort) vs. Pooled Sham, but where in all cases these p-values will be viewed as descriptive only. For the analyses of pooled RD-X19 vs. pooled Sham the log-rank test and the Cox proportional hazards models will each be stratified by cohort.

Following notations are used in the sample SAS code:

- TRT: treatment group with values 1 for RD-X19 from Final Cohort, 2 for RD-X19 from Cohort A, and 3 for Sham from Final Cohort, 4 for Sham from Cohort A
- TRTpooL: value 12 for pooled RD-X19 from both cohorts, 3 for pooled Sham
- COHORT: A for first cohort, B for Final cohort
- HOURS: time to sustained resolution of COVID-19 signs and symptoms
- CNSR: the censoring variables, 1 for censored, 0 for not censored
- COVIDSEV: grouping of COVID-19 Composite Severity Score at baseline, 1 for score <1.25, 2 for score  $\geq 1.25$
- DSSTATUS: baseline disease status, 1 for mild, 2 for moderate
- SEX: 1 for males, 2 for females
- AGEGRP: grouping of age, 1 for age <50, 2 for age  $\geq 50$
- ANTIBODY: grouping of baseline antibody status, 1 for positive, 2 for negative

Sample SAS Code for Main Analysis

1. Unstratified analysis of Primary Endpoint 1: Time to sustained resolution of COVID-19 signs and symptoms (in mild and moderate subjects)

a) RD-X19 from Final Cohort vs Sham from Final Cohort, log-rank test (unstratified)

```
PROC LIFETEST DATA=datain CONFTYPE=LINEAR;  
  WHERE trt in (1,3);  
  TIME hours*cnsr(1);  
  STRATA trt/ TEST=LOGRANK;  
RUN;
```

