## 5.6 Safety and Tolerability Variables and Analyses

Safety and tolerability analyses will be performed for the Safety Population. All safety tables will include summary statistics for each RD-X19 dose group, Pooled RD-X19 dose groups, and Pooled Sham.

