Note: Sustained resolution of COVID-19 signs and symptoms is defined as all 8 signs and symptoms (cough, sore throat, nasal congestion, headache, chills and/or sweats, myalgia, fatigue, and nausea) have been assessed by the subject as none (0) or mild (1) and all remain at or below 1 until study Day 14. Subjects reporting a persistent fever (100.5 degrees for 36 hours or more) and/or SpO2 levels <96% with any shortness of breath are considered not to have met the success criterion on that day even if all other symptoms are reported as none (0) or mild (1). Subjects who were hospitalized due to COVID-19 are designated as treatment failures, and right censored at 384 hours (16 days). Subjects discontinuing for other reasons are censored at their time of discontinuation. Other subjects who did not achieve sustained resolution at the last assessment of the study are considered censored at the time of the last assessment.

[1] Log-Rank Test and Cox PH Regression analyses were performed unstratified for RD-X19 from Cohort A vs. Pooled Sham, and stratified by cohort for Pooled RD-X19 vs. Pooled Sham.

[2] The Cox PH regression model included pre-specified covariates: COVID-19 Composite Severity Score at Baseline (<1.25,  $\geq$ 1.25)), Baseline Disease Status (mild, moderate), Sex (male, female), Age (<50,  $\geq$ 50), Baseline Antibody Status (positive, negative). For mFAS, the Cox PH regression model does not include the covariate related to baseline antibody status. Analyses were performed unstratified for RD-X19 from Cohort A vs. Pooled Sham, and stratified by cohort for Pooled RD-X19 vs. Pooled Sham.

Source: Listing 16.x.x

O:\Studies\EmitBio\EB-P20-01\Biometrics\Programs\Tables\xxx.sas ran on Month Day, Year at hh:mm on data from Month Day, Year.

Table 14.2.1.4 – Additional Supportive Analysis of the Second Primary Efficacy Endpoint: Time (Hours) to Sustained Resolution of COVID-19 Signs and Symptoms in Subjects with Mild Disease at Baseline, Both Cohorts Combined and RD-X19 from Cohort A

Population	Statistics	Pooled RD-X19	RD-X19 from Cohort A	Pooled Sham
Full Analysis Set (FAS)				
N		XX	XX	XX
n (%) Censored		XX (XX.X)	XX (XX.X)	XX (XX.X)
Median of Time to Sustained Resolution (95% CI)		XX.X (XX.X, XX.X)	XX.X (XX.X, XX.X)	XX.X (XX.X, XX.X)
25 th Percentile of Time to Sustained Resolution (95% CI)		XX.X (XX.X, XX.X)	XX.X (XX.X, XX.X)	XX.X (XX.X, XX.X)

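### The descriptive low-dose contrast sets Cohort A RD-X19, unstratified, against a pooled sham group that is about 86% non-concurrent, and most tables have no own-cohort sham column

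*SAP*

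**What the plan says.** **Design.** SAP 3.1 plans two sequential dosing cohorts, each with "20 assigned to RD-X19 and 10 assigned to sham per cohort, 2:1 randomization". Cohort B opens only after 80% of Cohort A has completed Day 8. The Final Cohort may then grow by up to 150 subjects at 2:1, of any serostatus, to as many as 180 (SAP 3.3).

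**Low-dose contrast.** SAP 5.5.1 repeats all primary-endpoint analyses "for RD-X19 low dose (i.e., the dose not expanded to produce the Final Cohort) vs. Pooled Sham", with descriptive p-values. The footnotes to Tables 14.2.1.3 and 14.2.1.4 add: "Log-Rank Test and Cox PH Regression analyses were performed unstratified for RD-X19 from Cohort A vs. Pooled Sham". Pooled RD-X19 against pooled sham is, by contrast, stratified by cohort. Protocol 10.4.1 foresees a low-dose analysis but names no comparator for it; pooled sham is the SAP's choice.

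**Default rule.** SAP 5.1 states: "The sham groups from different cohorts will not be combined for the analyses unless otherwise specified".

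**Tables.** For the primary analysis, "Tabulations will be displayed separately for RD-X19 and Sham from the Final cohort for the primary analysis". For safety, "All safety tables will include summary statistics for each RD-X19 dose group, Pooled RD-X19 dose groups, and Pooled Sham". The shells for disposition, populations, baseline, secondary efficacy, virology and safety have a single sham column, Pooled Sham. Figures 15.1.1b, 15.1.2b and 15.1.3b plot each dose against pooled sham.

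**The concern.** A Cohort A RD-X19 subject was randomised against Cohort A sham and nobody else. Most of the planned comparator for that dose was enrolled later, and the expansion admits subjects whatever their antibody status, whereas Cohort A recruits towards 30 seronegatives. If seropositive subjects resolve faster, or if circulating variants change between the two periods, the difference falls on the low-dose hazard ratio. The SAP treats cohort as a factor to control when both arms are pooled, but not in the one contrast where the arms differ most in cohort make-up.

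SAP section 2 sets out to establish evidence for each dose against sham, and the expansion is meant to prepare for future trials. What is at stake is therefore the dose-response reading. Calling the p-values descriptive does not take bias out of a hazard ratio, a Kaplan-Meier curve or a percentage.

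A second, practical loss is that Tables 14.1.1 to 14.1.3 have no column for Final Cohort sham. Baseline balance for the primary comparison cannot be read from them.

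**Working it through.** **1. The plan's own figures.** Final Cohort: 30 + 150 = 180, as stated. Power for the mFAS (60:30, 85%/75% events, 20% dropout, HR 0.4, one-sided 0.025): events = (60×0.85 + 30×0.75)×0.8 = 58.8; Schoenfeld power = 91%, which matches the stated minimum of 90%. The SAP gives no power or precision for the low-dose contrast.

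**2. Make-up of pooled sham at planned sizes.** Cohort A sham 10; Final Cohort sham 10 + 50 = 60; total 70.

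| Column compared with pooled sham | Sham from another cohort |
|---|---|
| Cohort A RD-X19 | 60/70 = 86% (10/20 = 50% without expansion) |
| Final Cohort RD-X19 | 10/70 = 14% |
| Pooled RD-X19 | balanced: Cohort A supplies 20/140 = 14% of RD-X19 and 10/70 = 14% of sham |

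The mFAS removes serostatus differences but not the time gap. With 90 to 105 Final Cohort seronegatives (30 to 35 sham), its pooled sham is 30/40 = 75% to 35/45 = 78% non-concurrent for the low dose.

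**3. Serostatus inputs.** SAP 3.3 expects about 90 of 180 Final Cohort subjects to be seropositive (50%). Taking 30 seronegatives plus an even split of the 150 gives 75/180 = 42%, so both are used. Cohort A's share is not given. Protocol 6.3 keeps its seropositives on treatment and under assessment, excludes them only from the mFAS, and enrols one extra subject for each.

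**4. Assumed event rates.** The SAP's planning rates for sham are 75% by Day 14 in the mFAS and 85% in the FAS. At a 50:50 mix, (75 + x)/2 = 85 gives x = 95% for seropositives. This is an inference, not a figure in the documents.

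**5. Hazard ratio with no treatment effect.** Simulated trials: 20 Cohort A RD-X19 against 10 + 60 sham, exponential times, follow-up to Day 14, Final Cohort 42% to 50% seropositive. The ranges span those two shares and repeated simulations of 1,500 to 3,000 trials.

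| Cohort A seropositive | Unadjusted FAS HR (>1 favours RD-X19) | Trials with z < −1.96 (nominal 2.5%) |
|---|---|---|
| 0% | 0.73–0.81 | 11–16% |
| 30% | 0.90–0.93 | 3–5% |
| same as Final Cohort | 1.00 | no distortion |

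In the 0% case, the antibody-adjusted Cox model gives HR 0.99–1.00 with z < −1.96 in 1.8–2.5% of trials; the mFAS gives 0.99–1.00 and 1.7–2.4%.

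With milder assumptions (seropositives resolving 1.25, 1.5 or 2 times as fast, Final Cohort 42% seropositive), the unadjusted HR is 0.93, 0.87 and 0.79 if Cohort A is 0% seropositive, and 0.96, 0.95 and 0.91 if it is 25%.

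**6. Final Cohort column.** Its own sham rate is 0.583×75 + 0.417×95 = 83.3%. Pooled sham, with Cohort A all seronegative, is (60×83.3 + 10×75)/70 = 82.1%. The shift is about 1 point.

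**7. Precision of the own-cohort contrast**, with the SAP's mFAS event and dropout assumptions; SE(log HR) = 1/√(events × p × (1−p)), where p is the RD-X19 share.

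| Contrast | Events | SE(log HR) | Power at HR 0.4 |
|---|---|---|---|
| 20 vs 10 | (17 + 7.5)×0.8 = 19.6 | 0.48 | 48% |
| 20 vs 70 | (17 + 52.5)×0.8 = 55.6 | 0.32 | 81% |

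**The case against.** **Serostatus is already handled where it counts most.** The low-dose analyses include a Cox model adjusted for antibody status and a seronegative-only mFAS analysis, and step 5 shows that either one removes the serostatus bias. The clinical and nasopharyngeal secondary endpoints also have mFAS tables. This stands. It does not reach the unadjusted FAS log-rank, Kaplan-Meier and Cox results, the FAS secondary summaries (SAP 5.5 makes the FAS primary there) or the safety tables, and none of it addresses calendar time.

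**The size is assumption-driven.** No eligibility criterion uses serostatus and Cohort A seropositives stay in the FAS, so 0% is an extreme case. The 95% rate holds only at a 50:50 mix; at 42% the same planning rates imply (85 − 0.583×75)/0.417 ≈ 99%. Nor are those rates coherent as exponential hazards: 85% against 75% implies a ratio of ln 0.15/ln 0.25 = 1.37, not the 2.5 that corresponds to the stated 0.4. This also stands. The direction is likely, the size uncertain.

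**Pooling breaks no rule.** SAP 5.1 permits it where specified, and it is specified. Section 6 allows the shells to be modified, and the listings identify cohort. Correct, but a planned table is still better than a reconstruction from listings.

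**Stronger readings.** A reader might infer that most comparisons with sham are non-randomised. Only the Cohort A column is. A reader might also infer that case mix is bound to make the low dose look worse, or that the trial's own dose choice is compromised. The first depends on a share that the documents do not give; as to the second, Protocol 10.2 bases the final-cohort dose on blinded data only.

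**Own-cohort sham is imprecise.** True, and a reason to show both contrasts rather than drop pooled sham.

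**Conclusion.** The point holds for one descriptive contrast and for the table layout. About 86% of the planned low-dose comparator is non-concurrent and was not randomised against that dose, and the analysis does not stratify for this. Calendar-time differences are uncontrolled in every version of the contrast; serostatus is uncontrolled only in the unadjusted FAS results, the FAS secondary summaries for the Cohort A column and the safety tables.

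The serostatus distortion could be substantial (inert-dose HR near 0.75), small (near 0.9) or absent, depending on Cohort A's seropositive share and on assumed event rates. The size of any calendar-time effect cannot be estimated from the documents.

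The primary test uses Final Cohort sham alone and is untouched. The Final Cohort dose and the pooled-dose comparison are not materially affected. This is an inexpensive improvement to the dose-response evidence, not a flaw in the main result.

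**What to change.** 1. In SAP 5.5.1 and Tables 14.2.1.3 and 14.2.1.4, report Cohort A RD-X19 against Cohort A sham beside the pooled-sham contrast, and label the latter as largely non-concurrent. Stratifying by cohort is equivalent for the log-rank test and the single-term Cox model, because the Final Cohort stratum contains no low-dose subjects.
2. Add columns for Final Cohort sham and Cohort A sham beside Pooled Sham in the disposition, population, baseline, secondary and safety tables.
3. Add a Cohort A sham curve to Figures 15.1.1b, 15.1.2b and 15.1.3b.

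The cost is SAP wording and extra columns; the SAS notation already codes the two sham groups separately (TRT 3 and 4). The statistical price is a wide interval for the own-cohort contrast (SE of log HR about 0.48 against 0.32), which is why both should be shown.

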**PROC LIFETEST DATA=**data**in PLOTS=SURVIVAL(FAILURE);**  
    **WHERE trt in (1,3);**  
    **TIME hours\*cnsr(1);**  
    **STRATA trt;**  
**RUN;**

### 5.5.2 Analysis of Secondary and Exploratory Endpoints

All secondary clinical, virologic, and exploratory efficacy endpoints will be summarized using descriptive statistics by visit (as appropriate) for each treatment group.

For virologic outcome assessments, subjects without a Baseline biospecimen collected and/or the Baseline biospecimen determined to NOT be an analysis-qualified sample, will be excluded from these analyses.

Analysis-qualified samples are defined as nasopharyngeal and saliva SARS-CoV-2 biospecimen samples that have no sample Violations as outlined in the Biospecimen Violation and Biospecimen Deviation (BVBD) Log. Any samples that are not analysis-qualified, designated by “Valid biospecimen = N” will be replaced by missing values (prior to the multiple imputation described below).

Viral load (log base 10 copies/mL) and cycle threshold (Ct) data are continuous in nature but may be reported as “undetermined” or “inconclusive” or “<LOQ”.

For analysis-qualified samples, results of “undetermined” and “<LOQ” for N1 copies/mL will be handled as follows for data summary purpose:

- For viral load reported as “Undetermined”, value 1 will be used to calculate descriptive statistics. This will support the need for logarithm transformation.
- For viral load reported as “<LOQ”, value  $5 \times 10^1$  will be used to calculate descriptive statistics.

Sample values reported as either “Inconclusive” N1 Ct viral load or with an “Undetermined” RNase P (RP) internal control Ct value will be replaced by missing values prior to the multiple imputation (MI) described below.

MI will be performed separately for saliva samples and nasopharyngeal samples and for each treatment via a two-step process for subjects with non-missing baseline. Viral load values will be log10-transformed before MI. Missing data occurring for an intermediate visit will be imputed first using a Markov Chain Monte Carlo (MCMC) method. As a result, a monotone missingness pattern will be obtained for the data to be fully imputed. The subsequent imputation will use Monotone Regression to produce 100 imputed datasets where the remaining missing data are filled in.

The SAS code for MI is as follows:

- Saliva samples: random number = 184962 as the seed for the first Step and 64849 as the seed for the second step.

- Nasopharyngeal samples: random number = 133274 as the seed for the first Step and 485044 as the seed for the second step.

Where notation of main variables:

- Log\_dayX: log10-transformed viral load at Day X visit, where X=1, 3, 5, 8 and 14.

\*Step 1: MCMC fills interim missingness to make monotone;

```
PROC MI data=datain out=step1 seed=XXXXXX n impute=100;
  mcmc impute=monotone;
  var log_day1 log_day3 log_day5 log_day8 log_day14;
run;
```

\*Step 2: MI regression;

```
PROC MI data=step1 out=step2 seed=XXXXXX n impute=1
  var log_day1 log_day3 log_day5 log_day8 log_day14;
  monotone reg(log_day3 = log_day1); *for D3;
  monotone reg(log_day5 = log_day1 log_day3); *for D5;
  monotone reg(log_day8 = log_day1 log_day3 log_day5); *for D8;
  monotone reg(log_day14 = log_day1 log_day3 log_day5 log_day8);
  by _imputation_;
run;
```

If either of the above multiple imputation procedures fails to converge, then multiple imputation (for both calls to PROC MI) will only be carried out for the Final Cohort, in which case only one of the 3 dummy variables for treatment will be needed in the first call to PROC MI.

The imputed values will be converted back to original scale by raising 10 to the power. For each missing value, its geometric mean of the 100 MI copies will be derived prior to the calculation of the summary statistics.

For log10-transformed viral load data, geometric means will be computed by exponentiating (base 10) the group means of the log10-transformed viral load.

In conjuncture with above handling of the viral data scenarios, for purposes of this protocol, clearance of viral infection post baseline visit is defined as achievement of: [1] RP Ct  $\geq 0$ , AND [2] Average N1 Ct = “Undetermined”.

Subjects with missing nasopharyngeal samples at any post baseline visit will not be imputed for the purposes of determining the proportion of subjects demonstrating clearance of viral infection. Such cases will be determined to be a ‘failure’ at this visit/assessment as having not achieved the endpoint of clearance of viral infection. If a subject’s nasopharyngeal SARS-CoV-2 biospecimen sample at Visit X had a Violation as outlined in the Biospecimen Violation and Biospecimen Deviation Log, the subject will also be considered ‘FAILURE’ at Visit X.

The sponsor may decide if oral microbiome samples for the exploratory oral microbiome assessment will be analyzed after database lock. Summary of microbial flora will not be included in this analysis plan.

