  - b) In the past 24 hours, have you returned to your usual activities (before your COVID-19 illness)?
- Proportion of study subjects with any one or more of the following severe clinical outcomes (including proportions of study subjects for each individual outcome):

- 1) who require medical attention or intervention attributed to COVID-19
- 2) who progress to severe systemic illness with respiratory rate  $\geq 30$ /minute, heart rate  $\geq 125$ , O2 saturation  $\leq 93\%$  on room air or PaO2/FiO2  $\leq 300$  mm Hg, or lung infiltrates upon imaging  $>50\%$ .
- 3) who require hospitalization for severe COVID-19
- 4) who require endotracheal ventilation or ECMO with or without the use of solumedrol
- 5) who die

Secondary virologic endpoints:

- Mean change in nasopharyngeal viral load on days 3, 5, 8, and 14
- Geometric mean nasopharyngeal viral load at baseline and on days 3, 5, 8, and 14
- Proportion of subjects demonstrating clearance of viral infection, defined as a negative nasopharyngeal swab via RT-qPCR as assessed on Days 3, 5, 8 and 14

Exploratory assessments of effects of RD-X19 in saliva viral load include:

- Mean change in saliva viral load on days 3, 5, 8, and 14
- Geometric mean saliva viral load at baseline and on days 3, 5, 8, and 14

Exploratory assessment of effects of RD-X19 in oral microbiome includes:

- Change in  $\alpha$  and  $\beta$  diversity in microbial flora from baseline on day 8 and day 14 as analyzed by 16S rRNA subunit analysis from frozen saliva samples

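### Viral-load means and geometric means are sensitive to an unjustified value of 1 copy/mL for undetermined results, and no check on that value is planned

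*SAP*

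**What the plan says.** The substitution rule in SAP Section 5.5.2 covers analysis-qualified samples. Results that are undetermined or below LOQ "for N1 copies/mL will be handled as follows for data summary purpose":

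- Undetermined: "value 1 will be used to calculate descriptive statistics. This will support the need for logarithm transformation".
- Below LOQ: "value $5 \times 10^1$ will be used to calculate descriptive statistics".

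The same section says that "geometric means will be computed by exponentiating (base 10) the group means of the log10-transformed viral load", so each substituted value enters the geometric mean directly. It also says "Viral load values will be log10-transformed before MI". Value 1 is the only number the SAP assigns to an undetermined result, so it appears to enter the multiple imputation as well.

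SAP Section 3.2 lists the affected secondary virologic endpoints: "Mean change in nasopharyngeal viral load on days 3, 5, 8, and 14" and "Geometric mean nasopharyngeal viral load at baseline and on days 3, 5, 8, and 14". The matching saliva measures are exploratory. SAP Section 5.5.2 summarises all of them descriptively, and Protocol Section 10.1 confines hypothesis testing to the two symptom-resolution endpoints.

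Clearance is handled separately. In SAP Section 5.5.2, "clearance of viral infection post baseline visit is defined as achievement of" a valid RNase P control together with an undetermined average N1 Ct. This is a category, and the substituted number plays no part in it.

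**The concern.** The stated reason for value 1 is that a logarithm can then be taken, which any positive number would allow. Neither document gives the assay's limit of detection or LOQ, so a reader cannot tell whether 1 or 50 resembles what the assay can distinguish. Two neighbouring assay outcomes end up 1.70 log10 apart without a reason for that distance. An undetermined sample is credited with a fall equal to its whole baseline log10 value.

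The SAP plans no censored-data model and no second substitution value. The planned tables would not show the problem either. The viral-load shells (14.2.3.x nasopharyngeal, 14.2.5.x saliva) give N, mean, SD, median, range and geometric mean, with no count of undetermined samples. For nasopharyngeal swabs the clearance tables (14.2.4.x) come close to supplying that count. For saliva there is no clearance table. A minimum of 0 would show only that at least one sample was undetermined.

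At stake is how far a reader can trust the reported size of the viral-load fall and the gap between arms, above all in saliva. Saliva is the specimen for which Protocol Section 4.1 reports 100-fold and 1000-fold reductions in the earlier trial, EB-P12-01.

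**Working it through.** The plan states no figure that depends on this rule, so there is nothing to reproduce first.

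**Inputs from SAP Section 5.5.2.** Undetermined = 1 (log10 = 0). Below LOQ = 50 (log10 = 1.699). Geometric mean = 10^(mean log10).

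**Inputs assumed.** The undetermined share p, the level of the other samples and the baseline level are not in the documents. The figures below leave imputed values aside.

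**Step 1, gap between the categories.** 50 / 1 = 50-fold; log10(50) − log10(1) = 1.699.

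**Step 2, effect on one arm's geometric mean.** Replacing 1 by c raises the mean log10 by p × log10(c) and multiplies the geometric mean by c^p.

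| p | shift in mean log10, c = 50 | factor, c = 50 | factor, c = 25 | factor, c = 10 |
|---|---|---|---|---|
| 10% | 0.170 | 1.48 | 1.38 | 1.26 |
| 20% | 0.340 | 2.19 | 1.90 | 1.58 |
| 50% | 0.849 | 7.07 | 5.00 | 3.16 |
| 80% | 1.359 | 22.87 | 13.13 | 6.31 |

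In an arm of 20, the planned RD-X19 size in Cohort A, reading one sample as undetermined instead of below LOQ is p = 1/20. That moves the geometric mean by 50^0.05 = 1.22-fold.

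**Step 3, effect on the between-arm ratio.** If the arms differ by d in undetermined share, choosing 1 over 50 multiplies the ratio of geometric means by 50^d: 1.22 at 5 points, 1.48 at 10, 2.19 at 20, 3.23 at 30. With equal shares the factor is 1.

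Worked case: RD-X19 60% and sham 40% undetermined, all other samples at 3 log10.

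- Value 1: means are 0.4 × 3 = 1.20 and 0.6 × 3 = 1.80. The sham/RD-X19 ratio is 10^0.60 = 3.98.
- Value 50: means are 1.20 + 0.6 × 1.699 = 2.219 and 1.80 + 0.4 × 1.699 = 2.480. The ratio is 10^0.260 = 1.82.
- 3.98 / 1.82 = 2.19, as the formula gives.

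**Step 4, share of the fall from baseline.** Assume a baseline of 6 log10 with no undetermined sample at baseline.

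| p | other samples (log10) | fall, value 1 | fall, value 50 | part due to the constant |
|---|---|---|---|---|
| 10% | 4 | 2.40 | 2.23 | 0.170 / 2.40 = 7% |
| 50% | 3 | 4.50 | 3.65 | 0.849 / 4.50 = 19% |
| 80% | 2.5 | 5.50 | 4.14 | 1.359 / 5.50 = 25% |

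Over assumed baselines of 5 to 7 log10 in these and similar cases, the part due to the constant runs from about 5% to 30%.

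**Scale.** SAP Section 5.5.2 labels viral load as log base 10 copies/mL just before giving these values. The reference to taking a logarithm, and the size of the below-LOQ value, show that 1 and 50 are on the original scale. The SAP should say so.

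**The case against.** The best defence is that the rule is prespecified, is the same in both arms and touches nothing that is tested. Equal viral-load distributions in the two arms give no spurious gap. The lower value for an undetermined result keeps the assay's order, and a swab that meets the SAP's own clearance definition plausibly carries less virus than one that does not. Setting both categories to 50 is also arbitrary: 50 is the substituted value, not a stated LOQ, and merging the categories only moves the spike in the imputation data from 0 to 1.70. The median is also tabulated, and it is unaffected unless about half or more of a group is undetermined.

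All of this stands. It is why 50 should not simply replace 1 as the sole derivation. It does not answer the point that the distance between the categories is unexplained and untested.

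A reader might go further in three ways, none of which the documents support:

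- That the geometric means are driven by the constant, or mainly reflect it. No undetermined share is given, and in the illustrations the constant accounts for a minority of the fall from baseline.
- That clearance is counted twice. Clearance is a separate binary endpoint, defined on Ct categories for nasopharyngeal swabs only, and is never combined with viral load.
- That a 20-point difference in undetermined share by itself creates a 2.2-fold ratio. Such a difference is itself a virologic difference. The 2.2 is only the multiplier from choosing 1 over 50.

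**Conclusion.** The point holds as one of sensitivity. Mean log10 changes and geometric means, nasopharyngeal and saliva, depend on a constant that the SAP neither justifies nor varies. The 50-fold gap is exact. Its effect depends on the undetermined share: slight when few samples are undetermined, large when most are, which is more plausible at Days 8 and 14 than early on. The between-arm contrast deserves most care, since it can roughly double under a 20-point difference in share. The factors also depend on the comparator, and are smaller against 10 or 25 than against 50.

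The consequence is confined to descriptive secondary and exploratory summaries. No primary test, significance level, power figure, sample size or clearance proportion changes. Fold reduction is not a named output of this SAP, although the mean log10 change carries the same information. The change should be made before unblinding, but the trial's main conclusion does not hang on it.

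**What to change.** In SAP Section 5.5.2:

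- State the laboratory's limit of detection and LOQ, give the reason for each substituted value, and say that both are in copies/mL before log transformation.
- Say which value an undetermined result takes in the multiple imputation.
- Prespecify an estimate that treats results below the assay limit as left-censored (a Tobit mean at the stated LOQ). At minimum, add a row that uses 50 copies/mL for every result below LOQ, including undetermined. Show it beside the value-1 summary in Tables 14.2.3.x and 14.2.5.x.
- In the same tables, report the number of undetermined and of below-LOQ samples by visit and arm, for both specimen types.
- Base any statement about the size of the viral-load reduction on results that hold under both versions.

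The cost is SAP wording, one LOQ figure from the laboratory, a derivation and some table rows. No new data are needed. Reported reductions may look smaller. When most samples are below the limit, a Tobit mean leans heavily on its assumed distribution, so the counts are needed whichever estimate is shown.
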